Since 2008, the Office of Suicide Prevention has maintained a registry of VHA suicide attempts and deaths reported by the Suicide Prevention Coordinators (SPCs) in each Medical Center. This active surveillance registry, VA-Suicide Prevention and Application Network (SPAN), was established to coordinate the identification and reporting of suicide-related events within and across facilities, to facilitate the identification of individuals at high risk to target interventions, and to support both program planning and evaluation. It has served as an important resource for planning the proposed study. Between April 1, 2010 and March 30, 2012, SPCs reported suicide attempts or deaths from suicide that became known to the facility in almost 30,000 Veterans utilizing VA services. Of these, 94% had a primary or secondary diagnosis of depression or bipolar disease documented in their medical records before the attempt or during the evaluation

of the attempt, and approximately half were first time attempters. Of these Veterans, 0.06% died within one week. Among those who survived, 15% reattempted suicide within a year, and approximately 3-5% died from natural or unnatural causes within one year. Suicide attempt survivors have a very high risk for repeated attempts and death.

Current VA Management of Suicidality

The VA's activities in suicide prevention constitute a comprehensive program that includes public health activities, ready access to high-quality health and mental health care services, and interventions targeting individuals at high risk. For those at risk, the program requires supplementing evidence-based treatment for underlying mental health conditions with interventions that directly address the risk of suicide. Documents defining the program are included as Appendix A.

The VA standard of care for the prevention-focused care of patients at high risk is specified in "Patients at High-Risk for Suicide," from the Principal Deputy Under Secretary for Health and the Deputy Under Secretary for Health for Operations and Management, April 24, 2008. This memo requires the Suicide Prevention Coordinator (SPC) at each facility to maintain a list of patients at high-risk for suicide, including, but not limited to those who have survived a suicide attempt. It includes specific language outlining requirements for the care for those at high-risk:

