A model in which impulsivity and aggression can serve as endophenotypes (deconstructed components of complex behavioral phenotypes) (Gottesman & Gould, 2003; Kovacsics et al., 2009, 2010; Mann et al., 2009; Ohmura et al., 2011; Turecki, 2005) for suicide underlies research on neurobiological mechanisms underlying suicide and the effects of lithium. Aggression and impulsivity can be evaluated in humans and animals; the same behaviors and traits that could serve as mediators in clinical populations could, from a different perspective, support the design of animal research on questions that are fundamentally human.

Although the proposed study is designed to improve suicide prevention and to decrease the public health burden of suicide, a rigorous test of the effectiveness of lithium could also catalyze research to probe mechanisms and to develop alternative agents.

II. SIGNIFICANCE OF THE PROPOSED RESEARCH TO THE VA

Suicide in Veterans is a major public health problem, a source of considerable anguish to families and communities, and a challenge to a health care system that already devotes substantial efforts and resources to solve the problem. The high rate of suicides and suicide attempts has persisted despite every effort to track the problem, enhance awareness and increase access to specialized mental health services and programs for veterans.

Each year, approximately 9,000 VA patients with bipolar disorder or depression who would be eligible for lithium treatment attempt suicide and survive. Based on data from SPAN and the CDC, 15% of those who survive attempts make a reattempt within one year, and approximately 0.5% die from suicide within one year (see below). The rate for reattempts is comparable to estimates from community studies, but the rate of deaths may be somewhat lower in VA (0.5% versus approximately 2%; Owens et al., 2002).

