If lithium treatment prevented approximately 40% of repeated attempts in patients with depression or bipolar disorder during the year after an attempt (see Section VII below), it would prevent almost 600 reattempts. If it prevented approximately 40% of deaths, it would save on the order of 20 lives each year. These estimates (and the others included below) are limited to the effects that would occur during one year of preventive treatment; they do not estimate the potential benefits of longer term maintenance treatment. However, the potential effect of lithium could be far larger. As discussed above, there are approximately 500 deaths from suicide each year in VA patients with depression or bipolar disorder. If lithium treatment were utilized in these patients, it could, in principle, lead to approximately 200 fewer deaths from suicide per year.

In considering the impact of lithium treatment, it is important to consider the potential effects on all-cause mortality among those who have survived a suicide attempt. There is substantial literature demonstrating that individuals who have survived a suicide attempt are at increased risk for death, not just from suicide, but from other forms of unnatural, external, or accidental deaths as well (Bergen et al., 2012; Cooper et al., 2005; Hawton et al., 1988, 2003, 2006; Karasouli et al., 2010; Nordentopf et al., 1993; Owens et al., 2002; Ostamo & Lonnqvist, 2001). One possible explanation for this finding may be that medical examiners and coroners may under-diagnose suicide; another is that there may be shared risk factors for suicide attempts and for death from unnatural causes.

In one preliminary investigation in the VA, 2276 patients who attempted suicide in the first quarter of 2009 were identified from the SPAN data set. Based on CDC data, 3.0% died during the subsequent year, 0.44% of the total died from suicide, and 1.30% from other unnatural causes. In another investigation in VA, 39,803 individuals were identified from medical record data as having survived a suicide attempt between 2000 and 2008. Based on CDC data, 14.8% had died by the end of 2009. 4.7% died within one year after their attempt, 0.80% from suicide

and 0.96% from other unnatural causes. For the 8331 Veterans identified from medical records as attempting suicide in 2008, 0.54% died from suicide in 1 year and 0.71% from other unnatural causes.

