As secondary objectives of the study, the efficacy of lithium will be evaluated for the prevention of subtypes of suicidal self-directed violence, for all suicidal self-directed violence events (even after the first recurrence), for the prevention of repeated events in subgroups as well as the entire sample, and to identify potential mediators.

The tertiary objective of the study is to extend the follow up period using electronically available data to describe patterns of lithium use following active participation in the study participants, as well as to evaluate rates and determinants of suicide reattempts and all cause mortality over a longer follow up period.

The study will enroll and randomize 1,862 patients to receive either lithium or placebo with enhanced usual care. The study is projected to run a total of 4.5 years with 3 years of recruitment, 1 year of follow-up on lithium or placebo, and time for start-up and closeout as indicated in the study budget. We expect to enroll, on average, 65 patients per site at 29 VA medical centers.

V. STUDY POPULATION

Inclusion Criteria

Admission of patients to CSP590 will require that:

1. They have survived an episode of suicidal self-directed violence (including suicide attempts and interrupted attempts; see below) that occurred within six months of initial consent to the study, or they were admitted to a mental health inpatient unit specifically to prevent suicide within six months of initial consent to the study.
2. They have a diagnosis of an affective disorder meeting DSM-IV-TR (2000) criteria for Bipolar I Disorder, Bipolar II Disorder, or current or recurrent Major Depressive Disorder. Meeting the diagnosis for a current Major Depressive Disorder requires the presence of a Major Depressive Episode (see below).
3. They are able and willing to identify one or more family members, friends, or other contacts and give permission for both clinical providers and the Research Team to contact them if the patient cannot be reached.
4. They are able to provide informed consent
5. There is concurrence from the patient's mental health provider about inclusion/exclusion criteria and confirmation of the providers' willingness to work with the research team in managing the patient during the course of the study (see below). The provider responsible for the patient's general medical care has been made aware of the participation

Rationale:

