The primary hypothesis is that lithium is superior to placebo for the prevention of episodes of suicidal self-directed violence, including suicide attempts, interrupted attempts, hospitalizations to prevent suicide, and deaths from suicide over the ensuing year. The primary outcome measure is time from randomization for treatment allocation to the first episode. The results for event-free survival will be analyzed by means of a two-sided log-rank test. The study will have one interim analysis and one final analysis.

The duration of the study will be 4.5 years total, which allows for 3 years of recruitment, 1 year of follow-up for all enrollees, and time for start-up and closeout as indicated. A total of 1,862 patients will be enrolled and randomized to receive either lithium or placebo, both in addition to

enhanced usual care. We expect to enroll an average of 65 patients per site at 29 VA medical centers. All subjects will be followed for 12 months after randomization. Section IX describes site identification and recruitment plans.

Estimated Incidence of Primary Endpoint

We posit a 1-year event rate of 15% in the placebo group for the primary outcome based on data from the literature on lithium and SPAN data.

Lauterbach et al. (2008) reported a 12% 1-year reattempt rate in the placebo group in a cohort primarily of women, slightly younger than the VA cohort, and predominantly with major depressive disorder. This rate is slightly lower than that projected for the current study possibly because hospitalizations to prevent suicide were not included. Oquendo et al. (2011) evaluated suicide attempts and suicide events separately. Reattempt rates at 1 year were approximately 12% and 18% in the lithium and valproate groups respectively. In spite of their small samples and a more rigid definition of the endpoint, these two trials provided point estimates of outcome event rates between 12% and 18%.

To obtain a more precise estimate of the event rate in the Veteran population, we used VA SPAN data from second half of FY 2010 through the first half of FY 2012 (24 months), to characterize the target Veteran population potentially eligible for the proposed study. Detailed analysis of this cohort is presented in Section IX and selected characteristics of this target population are included and compared to the participant profiles of prior studies in Table 2.

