Overall, there were 27,128 veterans with bipolar or major depressive disorder, who survived an attempted suicide between 4/1/2010 - 3/31/2012, a 24 month period. After considering exclusions for 6+ prior attempts, co-morbid conditions of schizophrenia, congestive heart failure, renal failure, lithium therapy within the past year, or use of medications that may interact with lithium, approximately 17,656 subjects (65%) remained potentially eligible for CSP590. According to SPAN data for a subset of the eligible cohort with at least one year of follow-up, 15.2% had repeated episodes of suicidal self-directed violence.

Using event rates from SPAN and the literature, we used a 12 month estimate of a 15% repeat rate in the control population to estimate our sample size and to determine feasibility.

Estimated Effect of the Intervention

In Table 2, we summarize key studies that provide estimates for the efficacy of lithium in reducing suicide rates in depression and bipolar populations. In their prospective cohort study of approximately 20,000 subjects with bipolar disorder, Goodwin et al. observed a 41% to 60% reduction in suicidal events for those on lithium compared to other pharmacological agents. In their meta-analyses of lithium studies, Cipriani and Guzzetta demonstrated larger effect sizes ranging from 74% to 88%. Together, these studies support estimates of effect sizes for lithium for reduction of suicide events of 50% or greater and we expect to observe a similar reduction in CSP590.

For the proposed study, however, Lauterbach's placebo-controlled clinical trial in a sample with a large proportion of patients with depressive disorders and Oquendo's valproate-controlled clinical trial in a sample of bipolar patients are also relevant. A reduction of 48% in 1-year reattempt rates in the lithium group relative to placebo was reported in the Lauterbach study, and approximately a 33% reduction in the lithium group relative to valproate group was observed in the Oquendo study.

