10.2. Futility Analysis

As a part of the interim futility analysis we will estimate the conditional probability (CP) of observing a significant final result based on assumptions about the distribution of future event rates. Assumptions for additional data to be collected in the second half of the study are:

- (1) “no-change” scenario where future event rates will occur at the same rate as currently observed rates,
- (2) “expected” scenario where future event rates occur at the rates expected at the beginning of the trial (i.e., as proposed in the protocol),
- (3) “extreme” scenario where future event rates occur at the currently observed overall event rate, but all new events occur in the placebo group so as to set the best scenario for achieving a significant difference.

For conditional probability estimation, we will use the estimation method developed by Proschan, Lan, and Wittes, 2006 and further described by Jitlal et. al, 2012, where

CP at a specific time = $1 - \Phi[(Z\alpha/2 - E[B(1)|B(t)])/\sqrt{1-t}]$,

$E[B(1)|B(t)]$ is the expected value of $B(t)$ at the end of the trial (when $t=1$), given the data observed until point t .

The information fraction, t , is the number of observed events so far, expressed as a proportion of the planned number of events.

11. Final Statistical Report

The final statistical report for CSP590 will be the submitted and accepted primary manuscript which includes results from the primary ITT analysis as outlined in section 4 and any additional analyses to be conducted based on the journal's peer review process. At minimum, the final statistical report will include the CONSORT diagram (section 8.3.1), descriptive characteristics of the ITT cohort (section 8.3.2), medical and psychiatric history of the cohort (section 9), and the primary analysis results (section 4.3).

12. References

- MacKinnon, D. P.; Lockwood, C. M. Hoffman, J. M., West S. G., Sheets V. A Comparison of Methods to Test Mediation and Other Intervening Variable Effects. *Psychological Methods* 7: 83–104, 2002

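### The 15% placebo rate rests largely on registry data counted from the suicide attempt, while the trial counts from randomisation months later; the gap is unadjusted, and events and power are overstated if reattempt risk falls with time.

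*Protocol*

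**What the plan says.** **Source of the rate.** Protocol Section I reports from the suicide surveillance registry: "Among those who survived, 15% reattempted suicide within a year". Section II repeats it: "15% of those who survive attempts make a reattempt within one year". Section VII (Estimated Incidence of Primary Endpoint) narrows this to potentially eligible patients: in "a subset of the eligible cohort with at least one year of follow-up, 15.2% had repeated episodes of suicidal self-directed violence". The same section turns this into the design assumption, "We posit a 1-year event rate of 15% in the placebo group for the primary outcome", citing the lithium literature as well as the registry. It presents the registry as the more precise source.

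**The trial's clock.** Section VII (Overview) states: "The primary outcome measure is time from randomization for treatment allocation to the first episode". SAP 4.2 agrees.

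**The gap.** Protocol Section V accepts an episode "that occurred within six months of initial consent to the study". SAP Table 1 says three months. Randomisation then follows a second consent, provider concurrence, laboratory tests and an EKG (Section XI).

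**What depends on the rate.** The 15% and 9.45% rates give the 182 events and 90% power in Table 3 (SAP Table 2). SAP 10.2 uses them again in futility scenario 2, where "future event rates occur at the rates expected at the beginning of the trial", and takes the planned number of events as the denominator of the information fraction.

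**Stated limitations.** Section VIII.B.2 names two influences on the repeat rate, study attention and closer surveillance. Time since the attempt is not among them.

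**The concern.** A one-year rate counted from the attempt includes the first weeks and months after it. Trial participants pass through part of that period before follow-up begins. The rate carries over unchanged only if the reattempt hazard is constant. If risk is highest soon after an attempt and then declines, the 12-month rate from randomisation is lower than 15%, fewer than 182 events will accrue, and power is below 90%. At the interim look, scenario 2 would credit too many future events, and an overstated event target would understate the information fraction, so the conditional power shown to the DMC would rest on the wrong inputs.

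**Working it through.** **1. Reproduce the plan.** Inputs: 15% and 9.45% (Section VII), 745 evaluable per arm (Table 3), two-sided final alpha 0.048 (SAP 10).

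- Hazard ratio = ln(1 − 0.0945)/ln(1 − 0.15) = 0.611; the plan states 0.61.
- Events = 745 × (0.15 + 0.0945) = 182, as stated.
- Power at 182 events: Schoenfeld 91%, Freedman 90%; the plan states 90%.

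The plan's arithmetic is sound. The question is only whether 15% is the right input.

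**2. Shift the time origin.** Assumption: time from attempt to reattempt is Weibull with shape k, fixed at 15% by one year, so the one-year cumulative hazard is −ln(0.85) = 0.1625. For a patient entering s years after the episode without a further event, the 12-month risk is

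p = 1 − exp{−0.1625 × [(1 + s)^k − s^k]}.

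Example with k = 0.7 and s = 0.25: 1.169 − 0.379 = 0.790; 0.1625 × 0.790 = 0.1284; p = 12.1%.

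The table averages this over entry spread evenly from 0.5 to 6 months (protocol window) or 0.5 to 3 months (SAP window), with the hazard ratio held at 0.611 and Schoenfeld power at alpha 0.048.

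| Shape k | Rate, to 6 months | Events | Power | Rate, to 3 months | Power |
|---|---|---|---|---|---|
| 1.0 (constant) | 15.0% | 182 | 91% | 15.0% | 91% |
| 0.9 | 14.1% | 171 | 89% | 14.4% | 90% |
| 0.85 | 13.6% | 165 | 88% | 14.0% | 89% |
| 0.7 | 12.1% | 146 | 84% | 12.8% | 86% |

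Freedman's formula, which tracks Table 3c, is about one point lower (83% to 88% for k = 0.7 to 0.9 with the six-month window). Table 3c itself gives 82% power at a 12% placebo rate.

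**3. What the documents say about the shape.** They contain no registry reattempt rates by time since the attempt. The indirect figures are these.

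- *Deaths over years (Section II).* "4.7% died within one year after their attempt", and 14.8% had died by the end of 2009, for attempts in 2000–2008. With attempts spread evenly, a constant hazard predicts 22.7%, and the fitted shape is 0.73. But Section II also reports 8,331 attempters in 2008. If they belong to the same cohort of 39,803 (not stated), 2008 holds 8,331/39,803 = 21%. The shape then rises to 0.77 (other years equal) or 0.89 (linear growth to 8,331).
- *Deaths in week one (Section I).* 0.06% in seven days is 0.06% × 365/7 = 3.1% annualised, against 3–5% over the year. That shows no early excess.
- *The valproate-controlled bipolar trial (Table 2).* In the valproate arm, one-year survival of 82% implies 18% with events, against 8/49 = 16.3% over all follow-up. If the 1.5 years listed is mean follow-up, a constant hazard gives 1 − exp(−8/73.5) = 10.3% at one year. This hints at early clustering, but it rests on 8 events.

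**The case against.** The strongest reply is that a net overstatement of power has not been shown. Several features could push the trial's rate up. The endpoint includes hospitalisation to prevent suicide. Repeated structured interviews may find more events (Section VIII.B.2), and registry attempts may be under-reported (Section VIII.B.1). A repeat attempt before consent does not exclude a patient; it becomes a new qualifying episode, subject to the limit on lifetime attempts. Recruitment from emergency and inpatient settings may keep many delays short. Two lithium trials with narrower endpoints gave one-year rates of 12% to 18% by arm. Table 3c reports power above 80% down to a 12% placebo rate, and Section VIII.B.2 already calls the repeat rate a limitation of the power calculation.

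Most of this stands. It limits the size of the point and leaves its net direction open. It does not remove the mismatch. The protocol says the attention and surveillance effects cannot be estimated, whereas the effect of the time origin can be, from data the sponsor holds.

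A reader might go further and infer that the protocol's own data show risk falling after an attempt. They do not. The long-run figures are all-cause deaths, and their apparent decline depends on how attempts were spread over the years. The week-one deaths point the other way. The bipolar-trial comparison sets a survival estimate against a crude proportion in an arm with 53% attrition, so the two cannot be subtracted to date events. A reader might also assume a steep fall (shape 0.5), which would give a rate of 9.6% and 73% power; no figure in the documents supports that shape.

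**Conclusion.** The concern holds in a conditional form. The registry rate is counted from the attempt, the trial counts from randomisation, and no section reconciles the two. The 182 events and 90% power are overstated if reattempt risk declines after an attempt, and correct on this point if it does not.

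Under the assumed shapes of 0.7 to 0.9 with entry 0.5 to 6 months after the episode, the loss is modest: a placebo rate of about 12.1% to 14.1%, 146 to 171 events and about 84% to 89% power. This lies within the rates that Table 3c already tabulates, although the lower end uses nearly all of the stated margin down to 12%. The shape and the entry distribution are assumptions, and the possible upward influences are not in the calculation.

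**What to change.** From the registry extract already held, re-estimate the 12-month repeat rate among potentially eligible patients, with time zero at landmarks of about 1, 3 and 6 months after the most recent qualifying episode. Weight the landmarks by the expected interval to randomisation. Reconcile the six-month window in protocol Section V with the three-month window in SAP Table 1, because the weights depend on it.

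If the result differs from 15%:

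- restate the placebo and lithium rates, expected events and power in the Executive Summary, Section VII, Table 3, and SAP 4.3 and 10;
- use the updated rates and planned events in SAP 10.2, both in scenario 2 and in the information fraction.

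In either case, add time since the index episode to the limitations in Section VIII.B.2.

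The cost is one re-analysis of existing data, some rewording, and possibly a slightly lower stated power. The sample size stays as it is.
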